3. STUDY DESIGN

3.1. Study Treatment Plan and Regimen

This is a randomized, double-blind, multicenter, active-controlled study to evaluate the safety and efficacy of TAF 25 mg QD in virologically suppressed subjects who switch from TDF to TAF compared to continued TDF treatment.

Approximately 460 subjects (with approximately 50% of subjects being \geq 50 years old) will be randomized in a 1:1 ratio (A:B) to receive either TAF 25 mg QD and matched placebo of TDF 300 mg QD or Gilead-provided TDF 300 mg QD and matched placebo of TAF 25 mg QD.

At randomization, subjects will be stratified by screening HBeAg status (HBeAg-negative vs. HBeAg-positive) and age (> 50 or < 50 years).

- Treatment Arm A: approximately 230 subjects administered TAF 25 mg QD and matched placebo of Tenofovir DF (TDF) 300 mg QD
- Treatment Arm B: approximately 230 subjects administered Gilead-provided TDF 300 mg QD and matched placebo of TAF 25 mg QD

The duration of double blind treatment is 48 weeks. All subjects who complete 48 weeks of treatment are eligible for participation in the open label TAF 25 mg extension period for an additional 48 weeks (through Week 96). During the double-blind period, subjects with a confirmed creatinine clearance by Cockcroft Gault Method (eGFR_{CG}) < 50 ml/min, and > 20% decline in eGFR by CKD-EPI (cystatin C) compared to baseline during the study, will be required to undergo dose modification to every other day dosing of study drug. Subjects with confirmed creatinine clearance < 30 mL/min during the double blind phase of the study will have the study drug permanently discontinued. Subjects with confirmed eGFR_{CG} < 50 mL/min will not undergo dose modification to every other day during the open-label TAF 25 mg extension period, nor will treatment be permanently discontinued for confirmed eGFR_{CG} < 30 mL/min during the open-label extension period.

Subjects who permanently discontinue study drug (either prematurely or at the end of study [Week 96]) for reasons other than HBsAg loss with confirmed seroconversion to anti-HBs will be followed every 4 weeks for 24 weeks off treatment or until initiation of appropriate alternative, HBV therapy, whichever occurs first. Use of appropriate, alternative HBV therapy is strongly encouraged.

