3.1.4. Treatment-Free Follow-up Safety Analysis Set

The treatment-free follow-up (TFFU) Safety Analysis Set includes all randomized subjects who entered the TFFU period. Subjects will be analyzed according to the treatment they actually received during the double-blind phase.

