3.1.7. TFFU Full Analysis Set

The TFFU FAS includes all randomized subjects who entered the TFFU period. Subjects will be analyzed according to the treatment to which they were randomized during the double-blind phase.

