3.2. Subject Grouping

For analyses based on the FAS, Open-Label FAS, and TFFU FAS, including the serologically evaluable FASs, subjects will be grouped according to the treatment to which they were randomized to during the double-blind phase. For analyses based on the Hip and Spine DXA Analysis Sets, Safety Analysis Set, Open-Label Hip and Spine DXA Analysis Sets, Open-Label Safety Analysis Set, and TFFU Safety Analysis Set, subjects will be grouped according to the actual treatment received during the double-blind phase.

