3.6.2. Analysis Windows

Subject visits might not occur on protocol specified days. Therefore, for the purpose of analysis, observations will be assigned to analysis windows.

The following windows (Table 3-1 to Table 3-6) apply only to baseline and postbaseline on-treatment assessments collected during the double-blind phase and open-label phase. For summaries and analyses, assessments will first be categorized into baseline and postbaseline on-treatment assessments occurring during the double-blind or open-label phase before applying analysis windows.

Baseline value for the double-blind phase is defined as the last nonmissing value obtained on or prior to Study Day 1. For DXA BMD, it is defined as the last value on or prior to Study Day 14.

For subjects who completed blinded study drug and entered the open-label phase, laboratory assessments that occurred during the period from Study Day 2 up to and including the minimum of the Last Dose Date of Blinded Study Drug + 3 days and Open-label Study Day 1, will be considered as postbaseline on-treatment assessments during the double-blind phase. If a subject prematurely discontinued blinded study drug or did not enter open-label phase after completion of blinded study drug, then postbaseline on-treatment assessments during the double-blind phase will be defined as assessments that occurred during the period from Study Day 2 up to and including the Last Dose Date of Blinded Study Drug + 3 days. DXA assessments that occurred during the period from Study Day 15 up to and including the Last Dose Date of Blinded Study Drug + 14 days will be considered as postbaseline on-treatment assessments during the double-blind phase.

Baseline value for the open-label phase is defined as the last nonmissing value obtained on or prior to Open-Label Study Day 1. For DXA BMD, it is defined as the last value on or prior to Open-Label Study Day 14.

For subjects who entered the open-label phase, postbaseline on-treatment assessments during the open-label phase will be defined as assessments that occurred during the period from Open-label Study Day 2 up to the Last Dose Date + 3 days. DXA assessments that occurred during the period from Open-label Study Day 15 up to the Last Dose Date + 14 days will be considered as postbaseline on-treatment assessments during the open-label phase.

Baseline value for the TFFU phase is defined as the last nonmissing value obtained on or prior to the Last Dose Date + 3 days.

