For baseline of the double-blind, open-label, and TFFU phases, the last available record on or prior to the first dose of blinded study drug, open-label study drug, and last dose date + 4 days will be selected, respectively. For DXA BMD baseline, the last value on or prior to Study Day 14 and Open-Label Study Day 14 will be selected for the double-bind and open-label phases, respectively. If there are multiple records with the same time or no time recorded on the same day for numeric observations, the average will be computed for that day, except for HBV DNA and quantitative HBsAg the geometric mean will be taken instead. If there are multiple records with the same time or no time recorded on the same day for categorical observations, the most conservative value will be taken, eg, negative will be selected over positive for HBeAg and HBsAg, and positive will be selected over negative for HBeAb and HBsAb.

The following specified rules will be used for postbaseline visits:

- **ALT:** The largest value will be included in the analysis when 2 or more ALT values occur within the same visit window.
- **BMD:** The latest record in the window will be selected
- **HBV DNA (IU/mL):** The record on the latest day in the window will be selected. If there is more than 1 record on the selected day, the geometric mean will be taken.
- Quantitative HBsAg (IU/mL): The record closest to the nominal day for that visit will be selected. If there are 2 records equidistant from the nominal day, the latest will be selected. If there is more than 1 record on the selected day, the geometric mean will be taken.
- **Serology:** For HBeAg, HBeAb, HBsAg, and HBsAb, the record closest to the nominal day for that visit will be selected. If there are 2 records equidistant from the nominal day, the latest will be selected. If there is more than 1 record on the selected day, the most conservative value will be taken, ie, positive will be selected over negative for HBeAg and HBsAg, and negative will be selected over positive for HBeAb and HBsAb.

For all other laboratory parameters:

• If multiple valid non-missing **numeric** observations exist in a window, then records will be chosen as follows:

The record closest to the nominal day for that visit will be selected. If there are 2 records equidistant from the nominal day, the latest will be selected. If there is more than 1 record on the selected day, the average will be taken.

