FibroTest score will be summarized using descriptive statistics (sample size, mean, SD, median, Q1, Q3, minimum, and maximum) by treatment group for subjects in the FAS. The p-value, differences in change from baseline in FibroTest score between the 2 treatment groups and the associated 95% CI will be constructed using ANOVA models, including treatment group, baseline HBeAg status (HBeAg-positive or HBeAg-negative) and age (< 50 or ≥ 50 years) as fixed effects in the model. A shift table of fibrosis stage from baseline based on the FibroTest score at Week 24, 48, and 96 will be provided. Mean change from baseline in FibroTest score will be plotted with 95% CI over time using observed data from baseline to Week 96. A listing of fibrosis assessment by FibroTest will also be provided.

All the analyses of the secondary efficacy endpoints, using both the M F and the M E approach, and plots described above will be repeated for subjects in the Open-Label FAS from open-label baseline to Week 96. No statistical comparisons will be performed.

For subjects in the TFFU FAS, only HBV DNA, ALT, HBsAg, HBeAg loss/seroconversion, and HBsAg loss/seroconversion endpoints will be summarized by visit in the TFFU phase as described above only using the M E approach. No statistical comparisons will be performed.

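### In the treatment-free follow-up summaries the TDF-arm group pools subjects who stopped blinded TDF with subjects who stopped open-label TAF; the follow-up baseline is also defined two ways

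*SAP*

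**What the plan says.** **Membership.** The TFFU Safety Analysis Set "includes all randomized subjects who entered the TFFU period" (SAP 3.1.4), and the TFFU FAS has the same membership (SAP 3.1.7). Protocol 3.1 shows who can enter: "Subjects who permanently discontinue study drug (either prematurely or at the end of study [Week 96]) for reasons other than HBsAg loss" and seroconversion are followed off treatment, so entry can come from either phase. Subjects who stop after HBsAg loss with seroconversion have their own off-treatment schedule (Protocol 6.4.1).

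**Grouping.** For the safety set, "Subjects will be analyzed according to the treatment they actually received during the double-blind phase" (SAP 3.1.4). For the FAS, "Subjects will be analyzed according to the treatment to which they were randomized during the double-blind phase" (SAP 3.1.7), and SAP 3.1.10 applies the same rule to the TFFU serologically evaluable sets. SAP 3.2 repeats it: for the "Open-Label Safety Analysis Set, and TFFU Safety Analysis Set, subjects will be grouped according to the actual treatment received during the double-blind phase".

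**Output.** SAP 6.2.2 lists HBV DNA, ALT, HBsAg and HBeAg outcomes for TFFU, and "HBsAg loss/seroconversion endpoints will be summarized by visit in the TFFU phase". SAP 7.1.7 adds post-treatment adverse events, and SAP 7.2.2.3 adds graded laboratory abnormalities.

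**Baseline.** SAP 3.6.2 says: "Baseline value for the TFFU phase is defined as the last nonmissing value obtained on or prior to the Last Dose Date + 3 days". SAP 3.6.3, on choosing among multiple records, takes the last available record on or before the relevant date, and for TFFU it reads: "and last dose date + 4 days will be selected, respectively".

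**The concern.** TFFU outcomes are anchored to the last dose. Follow-up days count from it (SAP 3.6.1), post-treatment adverse events begin after last dose + 3 days (SAP 7.1.6.1), and laboratory abnormalities are graded against the TFFU baseline (SAP 7.2.2.1). They are read as what happens when a drug is withdrawn, so the drug that matters is the one taken last.

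Double-blind arm does not identify that drug in the TDF arm. It does serve in the Open-Label sets (SAP 3.1.3 and 3.1.6), because each arm there corresponds to one sequence: TAF then TAF, or TDF then TAF. In the TFFU sets the TDF arm holds both TDF only and TDF then TAF. If off-treatment virologic, ALT or adverse-event patterns differed between the two drugs, the pooled column would blur the difference, and a post-treatment event after stopping TAF could sit in the TDF-arm group.

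The second issue is separate. With two baseline definitions, the same sample can be treated as baseline under one section and as follow-up under another.

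**Working it through.** The plan states no figure for the size or composition of the TFFU sets, so there is none to reproduce. The check is to trace the rules and then illustrate the mix.

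**1. Which drug is withdrawn**

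- SAP 3.6.1 sets the Last Dose Date to the last blinded dose for subjects who stopped blinded drug early, or who completed it but did not enter the open-label phase.
- For subjects who entered the open-label phase, it is the last open-label dose.
- After Week 48 the drug is TAF in both arms (Protocol 3.1 and 5.1).

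| Double-blind arm | Last dose in blinded phase | Last dose in open-label phase |
|---|---|---|
| TAF | TAF withdrawn | TAF withdrawn |
| TDF | TDF withdrawn | TAF withdrawn |

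The TAF row has one drug and the TDF row has two. None of the TFFU summaries in SAP 6.2.2, 7.1.7 or 7.2.2.3 splits by last drug or by phase of stopping. In SAP 4.1, entry into TFFU is a single disposition category by treatment group, so the tables do not reveal the mix.

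**2. How mixed the TDF-arm column could be (illustration)**

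Inputs:
- TDF arm: about 230 subjects (Protocol 3.1).
- Early stopping of blinded TDF: 21/432 = 4.9%, from the two earlier Phase 3 studies (Protocol 1.2.3). Using this rate here is an assumption.
- Assumed: all early stoppers enter TFFU, and everyone else goes on to open-label TAF.
- Assumed and varied: the share f of open-label subjects who enter TFFU.

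Stopped TDF: 230 × 21/432 = 11.2. Went on to TAF: 230 − 11.2 = 218.8.

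TAF share of the column = 218.8f / (218.8f + 11.2)

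| f | Stopped TAF | Stopped TDF | TAF share |
|---|---|---|---|
| 2% | 4.4 | 11.2 | 28% |
| 5% | 10.9 | 11.2 | 49% |
| 10% | 21.9 | 11.2 | 66% |
| 50% | 109.4 | 11.2 | 91% |
| 100% | 218.8 | 11.2 | 95% |

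The range widens if early stopping varies from 2% to 10% and the share of early stoppers entering TFFU from 50% to 100%:
- Low end (10% stop, all enter, f = 2%): 4.1 / (4.1 + 23.0) = 15%.
- High end (2% stop, half enter, f = 100%): 225.4 / (225.4 + 2.3) = 99%.

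Either drug could dominate.

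**3. The two baselines**

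| Place | Rule |
|---|---|
| SAP 3.6.2, baseline | up to last dose date + 3 days |
| SAP 7.2.2.1, TFFU baseline | up to last dose date + 3 days |
| SAP 3.6.2, post-treatment assessments | after last dose date + 3 days |
| SAP Table 3-7, first window | opens at last dose date + 4 |
| SAP 3.6.3, baseline record | up to last dose date + 4 days |

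Only SAP 3.6.3 differs. Under it, a value from the fourth day after last dose qualifies as baseline and also falls in the Follow-Up Week 4 window. Its change from baseline would be zero by construction, and a grade increase first seen that day would not register.

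**The case against.** The strongest defence is that grouping by original arm is a stated convention applied consistently across the SAP, and that it fixes who is grouped together, not what the column header says. This is right: the grouping is a problem of interpretation, not a contradiction. But a header such as TDF then TAF would be wrong for subjects who took only TDF, so relabelling alone does not separate the two kinds of withdrawal.

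Next, no objective or endpoint compares withdrawal of TAF with withdrawal of TDF. The TFFU efficacy summaries carry no statistical comparisons (SAP 6 and 6.2.2), and for off-treatment safety data the protocol asks only for separate summary or listing (Protocol 8.2.1.3 and 8.7). A split by last drug would not be a randomized contrast either, because early stoppers select themselves. All of this stands, and it limits the severity.

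The illustration is also open to challenge. The 4.9% comes from studies in a different population (median baseline HBV DNA 5.7 and 7.9 log10 IU/mL), not from suppressed switchers. Follow-up ends when alternative HBV therapy starts, which the protocol encourages, so full entry is an extreme. This too stands: the figures show that the mix is undetermined and estimate nothing.

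Finally, the baseline mismatch affects only samples taken exactly four days after last dose, and the early discontinuation visit is due within 72 hours of it (Protocol 6.5). Few samples should be involved, but the text still conflicts.

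**Conclusion.** The concern holds for the TDF-arm TFFU group only. As planned, its summaries mix withdrawal of two drugs in unknown proportion and cannot be read as describing either. Under the stated assumptions (230 subjects, 4.9% early stopping, all early stoppers entering) the TAF share lies between about 28% and 95%. The baseline conflict in SAP 3.6.3 is real and narrow. Severity is minor, and neither issue touches a primary or key secondary endpoint.

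A reader might infer more than the documents support:

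- That neither arm's TFFU output describes withdrawal. TAF-arm subjects take TAF in both phases, so that column does describe TAF withdrawal.
- That the study cannot report outcomes after stopping each drug. All efficacy and safety data from TFFU are listed (SAP 6 and 7), and last drug can be recovered from the dosing records behind SAP 3.6.1. The gap is in the summary tables.
- That the TDF-arm column is mostly TAF withdrawal. That depends on entry rates the documents do not give.
- That flares after TAF withdrawal would be tabulated under TDF. SAP 7.2.3 summarizes ALT elevations and flares for the open-label phase only; what could fall in the pooled group is a post-treatment adverse event or a graded ALT abnormality.

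**What to change.** 1. In SAP 3.1.4, 3.1.7, 3.1.10 and 3.2, split the TDF-arm TFFU group into two columns: last drug blinded TDF, and last drug open-label TAF. Leave the TAF-arm column as it is. Keep the output descriptive and add a footnote that the split is not randomized.
2. In SAP 3.6.3, change the TFFU baseline from last dose date + 4 days to + 3 days, matching SAP 3.6.2, SAP 7.2.2.1 and the start of follow-up in Table 3-7.

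The cost is SAP wording, one derived variable (drug at last dose) and table shells. Some cells may be small, particularly for last drug blinded TDF. Sample size, alpha and power do not change. If the SAP is already final, SAP 1 gives the route: document the change in the clinical study report.

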3.1.5. Full Analysis Set

The Full Analysis Set (FAS) will include all randomized subjects who have received at least 1 dose of study drug. Subjects will be analyzed according to the treatment to which they were randomized during the double-blind phase. This is the primary analysis set for efficacy analyses, unless otherwise specified.

3.1.6. Open-Label Full Analysis Set

The Open-Label FAS includes all randomized subjects who have received at least 1 dose of open-label study drug. Subjects will be analyzed according to the treatment to which they were randomized during the double-blind phase.

3.1.7. TFFU Full Analysis Set

The TFFU FAS includes all randomized subjects who entered the TFFU period. Subjects will be analyzed according to the treatment to which they were randomized during the double-blind phase.

3.1.8. Serologically Evaluable Full Analysis Set

3.1.8.1. Serologically Evaluable Full Analysis Set for HBeAg loss/seroconversion

The Serologically Evaluable Full Analysis Set for HBeAg loss/seroconversion will include all subjects who were randomized and had received at least 1 dose of study drug, and with HBeAg positive and HBeAb negative or missing values at baseline. Subjects will be analyzed according to the treatment they were randomized to during the double-blind phase.

3.1.8.2. Serologically Evaluable Full Analysis Set for HBsAg loss/seroconversion

The Serologically Evaluable Full Analysis Set for HBsAg loss/seroconversion will include all subjects who were randomized and had received at least 1 dose of study drug, and with HBsAg positive and HBsAb negative or missing values at baseline. Subjects will be analyzed according to the treatment they were randomized to during the double-blind phase.

3.1.9. Open-Label Serologically Evaluable Full Analysis Set

3.1.9.1. Open-Label Serologically Evaluable Full Analysis Set for HBeAg Loss/Seroconversion

The Open-Label Serologically Evaluable Full Analysis Set for HBeAg loss/seroconversion includes all subjects who were randomized and had received at least 1 dose of open-label study

drug, and with HBeAg positive and HBeAb negative or missing at open-label baseline. Subjects will be analyzed according to the treatment they were randomized to during the double-blind phase.

3.1.9.2. Open-Label Serologically Evaluable Full Analysis Set for HBsAg Loss/Seroconversion

The Open-Label Serologically Evaluable Full Analysis Set for HBsAg loss/seroconversion includes all subjects who were randomized and had received at least 1 dose of open-label study drug, and with HBsAg positive and HBsAb negative or missing at open-label baseline. Subjects will be analyzed according to the treatment they were randomized to during the double-blind phase.

3.1.10. TFFU Serologically Evaluable Full Analysis Set

3.1.10.1. TFFU Serologically Evaluable Full Analysis Set for HBeAg Loss/Seroconversion

The TFFU Serologically Evaluable Full Analysis Set for HBeAg loss/seroconversion includes all subjects who were randomized and entered the TFFU period, and with HBeAg positive and HBeAb negative or missing at TFFU baseline. Subjects will be analyzed according to the treatment they were randomized to during the double-blind phase.

3.1.10.2. TFFU Serologically Evaluable Full Analysis Set for HBsAg Loss/Seroconversion

The TFFU Serologically Evaluable Full Analysis Set for HBsAg loss/seroconversion includes all subjects who were randomized and entered the TFFU period, and with HBsAg positive and HBsAb negative or missing at TFFU baseline. Subjects will be analyzed according to the treatment they were randomized to during the double-blind phase.

3.1.11. DXA Analysis Set

3.1.11.1. Hip DXA Analysis Set

The Hip DXA Analysis Set will include all subjects who were randomized and had received at least 1 dose of study drug, and had nonmissing baseline hip BMD values. Subjects will be analyzed according to the treatment they actually received during the double-blind phase.

3.1.11.2. Spine DXA Analysis Set

The Spine DXA Analysis Set will include all subjects who were randomized and had received at least 1 dose of study drug, and had nonmissing baseline spine BMD values. Subjects will be analyzed according to the treatment they actually received during the double-blind phase.

3.1.12. Open-Label DXA Analysis Set

3.1.12.1. Open-Label Hip DXA Analysis Set

The Open-Label Hip DXA Analysis Set includes all subjects in the Open-Label Safety Analysis Set who had nonmissing open-label baseline hip BMD values. Subjects will be analyzed according to the treatment received in double-blind phase.

3.1.12.2. Open-Label Spine DXA Analysis Set

The Open-Label Spine DXA Analysis Set includes all subjects in the Open-Label Safety Analysis Set who had nonmissing open-label baseline spine BMD values. Subjects will be analyzed according to the treatment received in double-blind phase.

3.2. Subject Grouping

For analyses based on the FAS, Open-Label FAS, and TFFU FAS, including the serologically evaluable FASs, subjects will be grouped according to the treatment to which they were randomized to during the double-blind phase. For analyses based on the Hip and Spine DXA Analysis Sets, Safety Analysis Set, Open-Label Hip and Spine DXA Analysis Sets, Open-Label Safety Analysis Set, and TFFU Safety Analysis Set, subjects will be grouped according to the actual treatment received during the double-blind phase.

